PARTNERS HUMAN RESEARCH COMMITTEE PROTOCOL SUMMARY

Answer all questions accurately and completely in order to provide the PHRC with the relevant information to assess the risk-benefit ratio for the study. Do not leave sections blank.

PRINCIPAL/OVERALL INVESTIGATOR

[name]

PROTOCOL TITLE

Robotic-assisted therapy to improve manual dexterity in children with cerebral palsy: a pilot study on clinical outcomes and muscle synergies as a possible predictor of response.

FUNDING

Thrasher Research Fund

VERSION DATE

August 3rd, 2020

SPECIFIC AIMS

Concisely state the objectives of the study and the hypothesis being tested.

Aim 1. Assess the effectiveness of robot-assisted training on hand function and quality of life in children with CP.

Aim 2. To study the relationship between muscle synergies and the outcomes of robot-assisted training.

BACKGROUND AND SIGNIFICANCE

Provide a brief paragraph summarizing prior experience important for understanding the proposed study and procedures.

Pediatric cerebral palsy (CP) is a group of disorders affecting movement, development and posture leading to functional limitations. CP is the most common motor disorder in children (over 2 per 1 000 live births¹) and the leading cause of chronic childhood disability. It is attributed to non-progressive alterations occurring in the brain during fetal and newborn development². Clinical features of children with CP usually include weakness, spasticity, and loss of selective motor control³. Often, there are deficits in the integrity of neuroanatomical structures and pathways required for precision grasping and fine motor control of the fingers^{4,5}. As such, skilled finger movements and hand function do not develop normally⁶⁻⁸. This leads to severe limitations in activities of daily living (ADL)⁹⁻¹¹. The severity of impairments observed in children with CP is associated with deficits in specific domains of quality of life (QoL) (*i.e.* physical well-being, and social support and peers)⁹. Also, overall participation in ADL also has a significant impact on QoL (*i.e.* physical well-being, moods and emotions, and social support and peers)⁹. Therefore, not only should therapy focus on improving motor symptoms, it should aim to improve the performance of ADL.

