
In addition to assessing the efficacy of RAT, the proposed study aims to identify predictors of responsiveness to the intervention. This is of significance in order to adequately select children that will obtain the best outcome following IRTT as much variability can be observed in response to RAT. Baseline functional impairments have been shown to be important determinants of overall gross motor improvements following RAT of gait (*i.e.* more initial impairment → less improvements) suggesting that children may need to attain a certain level of motor function before being able to achieve optimal outcomes using RAT. While the current study also proposes to identify predictors of motor outcome following RAT using clinical outcome measures, we will also utilize a physiological measure (muscle synergies) that we have assessed to be a predictor of motor outcome following RAT of gait.

The scientific community widely accepts that the Central Nervous System (CNS) adopts several strategies to reduce the complexity of the control of movement⁴⁰⁻⁴⁴. Many authors have shown that one of these strategies consists in using a limited number of primitive signals undergoing the activation of muscles which, when combined, generate a full collection of movements⁴¹.

Some studies have shown that the sensitive nature of EMG to represent an aberrant motor control in CP⁴⁵. However, the assessment of muscle synergies during grasp has yet to be performed in this or any other population. Nonetheless, the similarity of gait synergies in CP, stroke, and

infant rhythmic-stepping indicates that there are common changes in control after brain injury that may reflect control in early development⁴⁶.

Whereas clinical measures of impairment in SMC are available⁴⁷, such measures do not provide information that is suitable to design physical therapy interventions aimed to address specific impairments and hence improve clinical outcomes of robot-assisted gait training.

If successful, the proposed approach would be expected to significantly improve clinical outcomes of manual dexterity in children with CP.

RESEARCH DESIGN AND METHODS

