Briefly describe study design and anticipated enrollment, i.e., number of subjects to be enrolled by researchers study-wide and by Partners researchers. Provide a brief summary of the eligibility criteria (for example, age range, gender, medical condition). Include any local site restrictions, for example, “Enrollment at Partners will be limited to adults although the sponsor’s protocol is open to both children and adults.”

A sample of 10 children with CP with no major orthopedic or neurological complications that could interfere with the robot-assisted training will be recruited in the study. This sample size was calculated for an F test with an effect size of 0.4, an alpha of 0.05, a beta of 0.80, a correlation coefficient between repeated measures of 0.7, and an attrition rate of 20%. A study clinician will screen potential subjects. Screening will include a standard history and physical exam to ensure subjects meet all entry requirements after consideration of inclusion and exclusion criteria. Specifically, [name], the study physician, will assess all subjects' suitability for using the Amadeo.

Inclusion criteria:

- Diagnosis of CP with upper-limb impairment
- 6 to 18 years of age.
- Manual Ability Classification Scale Level II or III.
- Ability to communicate pain or discomfort.

Exclusion Criteria:

- Recent use of upper-limb robotic-assisted training within the last 3 months.
- Contraindication to robotic-assisted manual training such acute and pronounced pain symptoms despite conventional pain therapy of the upper-limb, lack of compliance, high-grade ataxia, advanced osteoporosis, and fractures of the upper-limb.
- Modified Ashworth Scale (MAS) of 4 in the upper-limb.

Briefly describe study procedures. Include any local site restrictions, for example, “Subjects enrolled at Partners will not participate in the pharmacokinetic portion of the study.” Describe study endpoints.

All study procedures will take place in the Motion Analysis Laboratory at Spaulding Rehabilitation Hospital, Boston, Massachusetts, USA. Spaulding Rehabilitation Hospital is an affiliated hospital of Harvard Medical School.

Assessments

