Estimating the Number of Muscle Synergies: We will decompose the EMG matrix increasing the number of synergies up to the point where the reconstructed envelopes, obtained multiplying the synergy vectors by the temporal activations, have an average R^2 similarity with the EMG envelopes above 0.8 and a minimum R^2 similarity on the individual channel above 0.6.

Quantifying Synergy Similarity: Similarity between the synergies of each limb will first be assessed using the scalar product. We will further quantify synergy similarity by estimating the dimensionality of the subspace shared between the spaces spanned by the synergies of the two limbs by computing the principal angles between sets of synergy vectors and finding the number of principal angles whose cosines are greater than a threshold.

Statistical analyses: Results of the number of synergies, and similarity between limbs will be compared descriptively.

Assessing the relationship between muscle synergies and response to therapy: The relationship between changes in the Muscle Synergies and clinical scores (QUEST and Box and Block Test) will be investigated on a case by case basis evaluating the differences between the visits.

We will ask permission to study participants to video record them during the performance of the above-described clinical tests and the lab-based study.

Training:

Training will be performed using the Amadeo®. The computer-controlled device maintains patients' forearm in a secure position using Velcro straps. The patients fingertips are then

attached to the robotic device using mild adhesive tape (like a band aid). Patients then have to control interactive games displayed on the screen using their fingers.

- Each training session will include 30 minutes of active movements that can be divided into up to 3 bouts of 10 minutes depending on patient fatigue. During the training bouts, children will be encouraged to move continuously and as actively as possible. The Amadeo® provides several interactive games to facilitate motor learning. Between bouts, children will be allowed to rest for at least 5 minutes. Adjustments in training intensity will vary according to the children's ability and endurance. Training will take place up to 4 times per week for a total of 18 sessions over up to 7 weeks. Sessions will last approximately 60 minutes (including setup, training, and rest between each bout).

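### The title and Background ask what predicts response, but no planned analysis relates a pre-training measure to later outcome; the only linking analysis uses changes in synergies

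*Combined protocol and SAP*

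**What the plan says.** **The question posed.** The protocol title refers to "muscle synergies as a possible predictor of response". Background and Significance states that "the proposed study aims to identify predictors of responsiveness to the intervention" and gives the purpose: "in order to adequately select children that will obtain the best outcome following IRTT". Its precedent is a baseline measure: "Baseline functional impairments have been shown to be important determinants of overall gross motor improvements following RAT of gait". It extends the search beyond synergies: "the current study also proposes to identify predictors of motor outcome following RAT using clinical outcome measures". Expected Benefits mentions better patient selection as something that may eventually follow.

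**The formal aim.** Aim 2 is more general: "To study the relationship between muscle synergies and the outcomes of robot-assisted training". It names no baseline variable and no method.

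**The analyses planned.**
- Clinical tests: a descriptive summary of outcomes and a pre/post comparison.
- Lab-based study: a descriptive comparison of the number of synergies and of similarity between limbs.
- Lab-based study, on synergies and response to therapy: "The relationship between changes in the Muscle Synergies and clinical scores (QUEST and Box and Block Test) will be investigated", child by child, from the differences between assessments. No statistic is named.

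**The concern.** Choosing children before training needs a measure that is available before training. A change in synergies is not: it exists only once the child has finished the programme. Whether synergies and hand function change together is a reasonable mechanistic question, but it differs from whether baseline synergies, or baseline clinical scores, foretell outcome. One association can be strong while the other is weak or absent.

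Two things are at stake. The study could report concurrent change under a title that speaks of prediction. And if the baseline question is taken up only after the data are in, the predictor, outcome and limb will be chosen with results in view. There is room for that. The Lab-based study section offers three synergy summaries (number, scalar-product similarity, and shared dimensionality at a threshold it does not state), in two limbs, with two clinical tests.

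**Working it through.** **1. Objective against analysis.**

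| Stated intent | Needs | Planned analysis |
|---|---|---|
| Synergies as possible predictor (title, Background) | Baseline synergy measure against later outcome | Change in synergies against QUEST and Box and Block |
| Clinical measures as predictors (Background) | Baseline clinical score against later outcome | Descriptive pre/post comparison only |
| Relationship of synergies to outcomes (Aim 2) | Any stated association | Change in synergies against QUEST and Box and Block: fits |

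The wording of the linking analysis is ambiguous: the word for change may apply to synergies alone or also to the clinical scores. On either reading the synergy term is a change, not a baseline value.

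**2. The plan's own figure.** The sample size of 10 (Research Design and Methods) rests on an F test with effect size f = 0.4, alpha 0.05, power 0.80 (the text calls this beta), "a correlation coefficient between repeated measures of 0.7", and 20% attrition. The number of measurements m is not stated. For a one-group repeated-measures F test with sphericity, the noncentrality is f² × N × m / (1 − rho). With m = 3 and N = 8 this is 0.16 × 8 × 3 / 0.3 = 12.8 on 2 and 14 degrees of freedom, giving power 0.825; then 8 / 0.80 = 10. So the figure reproduces if three measurements are assumed. It sizes a comparison over time, not a predictor analysis. For scale, 80% power for a true simple correlation of 0.5 needs ((1.960 + 0.842) / 0.549)² + 3 ≈ 29.01, so 30 children.

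**3. Can the change analysis stand in for the baseline one?** This is an illustration only, since the documents give no correlation for synergies. Let S0 and S1 be the synergy measure before and after training, with equal variances and repeat correlation rho. Assume corr(S0, gain) = 0.70 and that synergy change is related to gain only through its link to S0. Then

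corr(S1 − S0, gain) = 0.70 × [−√((1 − rho) / 2)]

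- rho = 0.5: 0.70 × (−0.500) = −0.35
- rho = 0.7: 0.70 × (−0.387) = −0.27
- rho = 0.9: 0.70 × (−0.224) = −0.16

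The converse is symmetric. If gain correlates 0.70 with synergy change, and baseline matters only through that change, the baseline-to-gain correlation at rho = 0.7 is −0.27. The 0.7 is borrowed from the sample-size text and is not a measured repeatability of synergies, hence the range.

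**4. Coupling.** The bracketed term above is also the correlation between a test's baseline and its own change when nothing predicts gain: −√((1 − 0.7) / 2) = −0.39 at rho = 0.7 with equal variances. A baseline analysis should therefore use the post-training score adjusted for baseline.

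**5. Precision of an added analysis.** For an observed partial correlation of 0.5 with one covariate, Fisher's z is 0.549 with standard error 1/√(n − 4).
- n = 10: 0.549 ± 1.96 × 0.408 = −0.251 to 1.349, so r from −0.25 to 0.87
- n = 8 (10 less 20% attrition): 0.549 ± 1.96 × 0.500 = −0.431 to 1.529, so r from −0.41 to 0.91

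**The case against.** The best defence is that this is a small pilot described in a brief review-board summary, with every analysis descriptive. The title says only that synergies are a possible predictor. The formal objective, Aim 2, asks only for a relationship, and the planned comparison delivers one. The predictor language sits in Background, and better selection is offered as an eventual hope. A child-by-child review does not prevent anyone from looking at baseline values, and baseline clinical data are collected anyway. Even a repaired analysis could not justify selecting children at this sample size.

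Much of this stands, and it limits the seriousness of the point. It does not supply the missing analysis. Background states outright that the study aims to identify predictors and says what they are for, and nothing planned uses a pre-training measure in that way.

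A reader might infer more than the documents support:
- *That Aim 2 has no analysis.* It has one; the gap is with the title and Background.
- *That the planned comparison would probably overlook a strong predictor.* The documents give no synergy correlations, and with 8 to 10 children a small observed correlation is common even when no association exists. The illustration shows that the two questions differ; it does not give a probability of missing anything.

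**Conclusion.** The point holds as a modest mismatch between objective and analysis. The title and Background pose a question about pre-training measures, and no planned analysis relates any baseline measure, synergy or clinical, to later outcome. This rests on the text alone. The figures of −0.16 to −0.35 rest on an assumed baseline-to-gain correlation of 0.70, equal variances, repeat correlations of 0.9 to 0.5, and no separate effect of synergy change on gain. They show only that the planned analysis is no substitute. The pre/post comparison of outcomes is unaffected.

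**What to change.** Either of two changes is enough.

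**(1) Add a short exploratory analysis to the Lab-based study section.**
- Name one lead pair beforehand. An example is baseline between-limb synergy similarity against post-training Box and Block in the trained hand, adjusted for baseline Box and Block. The trained hand should be recorded for each child, since the documents do not define it.
- Show other baseline synergy and clinical measures in the same way, as secondary displays.
- Report per-child plots and estimates with 95% intervals, not tests. Do not correlate a test's baseline with its own change.
- State that the lab session is done at baseline and after training; the text only implies this by referring to differences between visits.
- Label the results hypothesis-generating, and say that without a control arm they cannot separate response to training from general prognosis.
- Keep the comparison of changes as a mechanistic description.

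Cost: a paragraph of text and a little code, with no new visit if the lab session is done at baseline as implied. The intervals will be very wide, so the result cannot by itself support selecting children.

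**(2) Reword the title and the Background objective** as describing concurrent change in synergies and hand function. Cost: wording only, but it gives up the predictor question.

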Once the children are enrolled in the study, they will undergo a baseline assessment before undertaking a 6 weeks/18 sessions RAT program. Once training is completed, the children will undergo a final assessment. Finally, a follow-up assessment will be performed one month after the end of the RAT program to evaluate retention in the quality of life.

The follow up assessment will be performed 4 weeks after the end of the intervention and will consist in the cerebral palsy Quality of Life Questionnaire, which it will be provided to the subjects and they will be asked to fill it out and return to us when completed by email or mail (note: the questionnaire does not include any identifiable information).

Clinical tests

Clinical tests will be conducted by a study staff before and after the intervention. Clinical testing should last about 1 hour and will include:

- Physical examination: we will gather measures of Range of Motion (ROM) and muscular strength for the upper extremities. Passive and active movements of the shoulder (flexion, extension, abduction and adduction), elbow (flexion and extension), radioulnar joint (pronation and supination), wrist (flexion, extension, abduction, and adduction), and fingers (flexion, extension, abduction, and adduction) will be assessed with a goniometer.
- Modified Ashworth Scale (MAS)^{48,49}: We will assess spasticity at the shoulder (flexion-extension); elbow (flexion-extension); radioulnar (pronation-supination), and wrist (flexion-extension).
- Quality of Upper Extremity Skills Test (QUEST): this standardized test is a validated and reliable tool to evaluate movement patterns and hand function in children with cerebral palsy. The QUEST evaluates quality of upper extremity function in four domains: dissociated movement, grasp, protective extension, and weight bearing.
- Box and block test⁵²: this test assesses unilateral gross manual dexterity. Children are seated at a table, facing a rectangular box that is divided into two square compartments. The individual is instructed to move as many blocks as possible, one at a time, from one compartment to the other for a period of 60 seconds.

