- The cerebral palsy Quality of Life Questionnaire⁵³: this standardized test assesses 7 domains related to quality of life (social wellbeing and acceptance, feelings about functioning, participation and physical health, emotional wellbeing and self-esteem, access to service, pain and impact of disability, and family health) and was specifically developed for children between 4-12 years of age with cerebral palsy. It is designed for self- and parent proxy report.
- *Statistical analyses*: We will perform a descriptive analysis of the different outcome measures and compare results between pre and post intervention.

Lab-based study

We propose to analyze the muscle synergies of subjects using a method developed by members of the Motion Analysis Laboratory and their collaborators^{41,54-60}. Subjects will be asked to reach and grasp objects of different sizes and shapes. Electromyographic (EMG) activity will be collected from 16 muscles of the upper-limb (*i.e.* Teres Major, Infraspinatus, Superior trapezius, Deltoid anterior/posterior, clavicular head of Pectoralis major, Triceps brachii lateral head, Biceps brachii (long head), Brachioradialis, Extensor digitorum communis, Extensor carpi radialis longus, Flexor carpi radialis, Flexor carpi ulnaris, First dorsal interosseous, Abductor pollicis brevis, Abductor digiti minimi). This same procedure will be replicated contralaterally. Additionally, reflective markers will be placed bilaterally on the subjects' upper-limbs (*i.e.* C7, T10, Manubrium sterni, Xiphoid process, Acromion, Lateral epicondyle, Styloid process of the radius, Styloid process of the ulna, distal head of the first/second/third/fourth/fifth metacarpus, distal head of the first/second/third/fourth/fifth proximal and distal phalanges, and distal head of the second/third/fourth/fifth middle phalange) in order to assess movement kinematics. The entire process should last approximately 1.5 hour.

Extracting Muscle Synergies: Muscle synergies and their activation coefficients will be extracted from the EMGs using a nonnegative matrix factorization (NMF) algorithm. The NMF models the activity of the muscles as a linear combination of several muscle synergies, each activated by a time-dependent coefficient. Synergies will be extracted separately from the EMGs of each limb. A first estimate of the number of synergies of each limb will be obtained based the quality of reconstruction of the original EMG channels.

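### Aim 2 asks a question across children, but the plan reads changes child by child and names no pairing, so it yields no estimate of the relationship and no measure of its uncertainty.

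*Combined protocol and SAP*

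**What the plan says.** Specific Aims, Aim 2: "To study the relationship between muscle synergies and the outcomes of robot-assisted training". Background and Significance gives the purpose: "the proposed study aims to identify predictors of responsiveness to the intervention", so that the children who stand to benefit most can be selected. The title calls synergies a possible predictor of response.

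The analysis is in the Lab-based study section. On synergies alone: "Results of the number of synergies, and similarity between limbs will be compared descriptively". On the link with therapy response, changes in synergies and in "clinical scores (QUEST and Box and Block Test") "will be investigated on a case by case basis evaluating the differences between the visits".

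The same section defines several synergy summaries. "Synergies will be extracted separately from the EMGs of each limb", which gives a number of synergies per limb. Similarity between limbs is measured by a scalar product and by the dimension of a shared subspace, with an unspecified cosine threshold. Under Clinical tests, QUEST is described as scoring function "in four domains: dissociated movement, grasp, protective extension, and weight bearing"; the plan does not say whether a total or the domains will be used.

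No section names a correlation, model, plot or interval for Aim 2, a leading synergy measure, a leading score, or a rule for what counts as a match.

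**The concern.** A relationship between synergy change and clinical gain is a property of the group. A single child contributes one point, and a point has no slope. Reading the children one at a time can describe each of them well and still leave Aim 2 unanswered. It also leaves the next study without a correlation, or a range for one, to plan from.

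The open pairing adds a second problem. With several synergy summaries and at least two scores, whoever reads the cases can choose afterwards which pair to describe. Nothing in the plan lets a reader tell a pairing named in advance from the best-looking of many.

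A case-by-case reading also cannot show whether an apparent link merely follows how impaired the children were at the start. The Background raises a related possibility, though only for gait: "Baseline functional impairments have been shown to be important determinants of overall gross motor improvements following RAT of gait".

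**Working it through.** **The plan's own figure.** The only numerical planning is the sample size of 10 in Research Design and Methods, for a repeated-measures F test with effect size 0.4, alpha 0.05, correlation 0.7, attrition 20%, and a stated beta of 0.80 that I read as power. The number of measurements m is not given. With noncentrality f² × n × m / (1 − ρ) and m = 3, n = 8 gives 0.16 × 8 × 3 / 0.3 = 12.8 on 2 and 14 degrees of freedom, and power 0.825. Then 8 / 0.8 = 10, which reproduces the figure. It concerns change over time; no figure is given for Aim 2.

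**Children available.** 10 × (1 − 0.20) = 8 completers.

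**Pairings.** The plan fixes no count, so this is my inference.

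- Synergy measures: number of synergies in each limb (2), scalar-product similarity (1), shared-subspace dimension (1), total 4.
- Scores on the plain reading: QUEST and Box and Block, so 4 × 2 = 8 pairings.
- If the four QUEST domains were used separately: 4 × (4 + 1) = 20 pairings.

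**If the pairings were screened at the 5% level.** For independent tests the chance of at least one false match is 1 − 0.95^k: 1 − 0.95^8 = 0.34 and 1 − 0.95^20 = 0.64. The pairings share measures and children, and Spearman's coefficient is discrete at n = 8 (two-sided critical value 0.738). I therefore simulated 8 children with no true relationship, at several correlations among the measures within each set. Ranges cover repeated simulation runs.

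| Within-set correlation | 8 pairings | 20 pairings |
|---|---|---|
| 0 | 30–32% | 60–61% |
| 0.5 | 27–28% | 50–51% |
| 0.7 | 22–23% | 40–41% |

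Three of the four synergy measures are integer counts and will tie. Treating their changes as −1, 0 or +1 gives 20% to 29% for 8 pairings and 36% to 57% for 20. One pairing named in advance stays at or just below 5%; with a heavily tied count it is about 3% to 4%.

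**What a named pairing would deliver.** Fisher z with standard error √(1.06 / (n − 3)) = √(1.06 / 5) = 0.460. For an observed 0.5, z = 0.549, and 0.549 ± 1.96 × 0.460 is −0.353 to 1.452. Back-transformed, the 95% interval is −0.34 to 0.90. Power at n = 8 for a true correlation of 0.7 is about 0.41.

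**The case against.** This is a labelled pilot with 8 to 10 children, and describing cases is a defensible way to look at so few. The repair buys little inference: the interval is wide and power is low. That stands, and it is why the result should be presented as planning information. It does not remove the mismatch. A pilot can be descriptive and still summarise across children, and a scatter plot with one correlation is itself description.

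A reader might infer more than the documents support in three ways.

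- *That a chance match is likely.* At the 5% level this needs roughly 20 pairings whose measures are not strongly correlated. The plan lists the QUEST domains but nowhere says they will be analysed separately. On the 8-pairing reading the chance is below one in three.
- *That the plan runs such a screen, or that a chosen match will be reported as a finding without its uncertainty.* The plan states no test, threshold or match criterion, and it does not say how any link will be worded. The percentages describe a hypothetical screen.
- *That the protocol says baseline severity drives gain from hand training.* Its statement is about gross motor gains after robotic gait training, from which it draws only a suggestion. It is a reason to show baseline level on the plot, not evidence that severity explains any link here.

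**Conclusion.** The concern holds in this form: the method stated for Aim 2 cannot answer Aim 2, because no section supplies an across-child summary or its uncertainty, and the choice of pairing is left open. That part rests on the text alone.

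The size of the selection problem rests on assumptions: 8 completers, four synergy measures, and screening at 5% with no true relationship. It is about 22% to 32% with two scores, and about 40% to 61% if QUEST is split into its four domains; ties pull both ranges down somewhat. The documents do not support saying that a spurious match is more likely than not.

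The change is worth making because it costs little, but it will not confirm a predictor. The plan compares change with change; whether baseline synergies predict response is a separate question that this point does not settle.

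**What to change.** In the Lab-based study section, replace the case-by-case sentence with one pairing that the investigators fix before analysis.

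- **Synergy side:** for example, change in between-limb scalar-product similarity, which is continuous and so ties little. The rule that reduces it to one number per child should be written down. If a single-limb measure is wanted, use change in the number of synergies of the trained limb, accepting ties; the two similarity measures are both between limbs.
- **Clinical side:** change in one named score, either Box and Block of the trained hand or QUEST total.
- **Report:** Spearman's correlation across all children with a 95% interval and a permutation p-value that allows for ties, plus a scatter plot labelling each child with baseline score and MACS level.
- **Everything else:** list all other pairings in one table marked exploratory, keep the case descriptions as illustration, and state that the result is for planning only.

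The cost is a few sentences of analysis text and a few lines of code, on data already to be collected. The downside is that a wide interval will be on view.
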